#### **9.3.6.1 Analysis**

Pairwise comparison as Cochran Mantel Haenszel test adjusted by surgical procedure will be applied to the proportion of patients who completed the study up to at least Day 4 with nausea occurring at least once between Day 4 and discharge defined in (1) of section 9.3.5.

### **9.3.7 Proportion of Patients with Vomiting on Day 4 through Day of Discharge**

Vomiting will be as reported as an adverse event. The proportions described in section 9.3.6 will be calculated for vomiting.

### **9.3.7.1 Analysis**

The proportion will be analyzed in the same way as described in section 9.3.5.1.

### **9.3.8 Proportion of Patients who Achieve GI2 in Each Treatment Group by Postoperative Day**

The proportion of patients who achieved GI2 by study day will be calculated by treatment group. The denominator will be the number of patients who stayed in the study by each study day.

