9.4.5 Efficacy Analyses

The mITT Population will be the primary population for efficacy analyses.

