## **5. ANALYSIS POPULATIONS**

### **5.1 Modified Intention-to-treat Population**

The mITT Population will include all randomized patients who received at least 1 dose of study treatment and had at least 1 postbaseline efficacy assessment for the primary efficacy endpoint, which includes all three components (end of surgery time, time when the patient first tolerates solid food, and time of first bowel movement) of the time to event of GI2. Patients will be analyzed according to the treatment to which they were randomized.

This population will be the primary efficacy analysis population.

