## 6.4 Missing Data

Missing values will not be imputed. All statistical analyses will be based on observed cases unless otherwise noted.

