## 9. EFFICACY

Efficacy analyses will be performed for the mITT population unless otherwise specified.

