### **9.2.2.1 Analysis**

Pairwise comparison as Cochran Mantel Haenszel test adjusted by surgical procedure will be applied to the proportion.

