#### **9.3.8.1 Analysis**

The proportion will be analyzed at each postoperative day in the same way as described in section 9.2.2.1.

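### SAP 9.3.8 divides the day-by-day GI2 proportion by patients still in the study, so a patient who leaves unrecovered raises the arm's figure

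*SAP*

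**What the plan says.** SAP 9.3.8 defines the numerator: "The proportion of patients who achieved GI2 by study day will be calculated by treatment group". The denominator follows: "The denominator will be the number of patients who stayed in the study by each study day". SAP 9.3.8.1 adds the testing: "The proportion will be analyzed at each postoperative day in the same way as described in section 9.2.2.1". Section 9.2.2.1 reads: "Pairwise comparison as Cochran Mantel Haenszel test adjusted by surgical procedure will be applied to the proportion". SAP 6.2 sets the two-sided 0.05 level with no multiplicity adjustment.

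The surrounding rules are these:

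- **Population.** Protocol 9.4.5: "The mITT Population will be the primary population for efficacy analyses". SAP 9: "Efficacy analyses will be performed for the mITT population unless otherwise specified". The Protocol lists this endpoint (Sections 3 and 9.4.5.3) without any condition on remaining in the study.
- **mITT definition.** SAP 5.1 requires that the patient "had at least 1 postbaseline efficacy assessment for the primary efficacy endpoint, which includes all three components" of the time to GI2 (end of surgery, food, bowel movement).
- **Missing data.** SAP 6.4: "Missing values will not be imputed. All statistical analyses will be based on observed cases unless otherwise noted". Nothing in 9.3.8 says how an unrecovered leaver is counted.
- **Related table.** SAP 9.1.2 plans another cumulative GI2 proportion by day. It treats GI2 as sustained once achieved, up to Day 10, withdrawal or discharge, and states no denominator. Protocol 9.4.5.1 describes a cumulative by-day proportion of patients in each group.

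**The concern.** Being in the study on a given day is a post-randomisation event. Dividing by those who remain conditions the comparison on that event. Protocol 7.2 permits withdrawal for safety, at the patient's request, and for behavioural, compliance or administrative reasons. Some of these can depend on dose or on persistent gut dysfunction. If unrecovered patients leave one arm more than another for such reasons, the day-specific CMH tests compare selected subsets, and the error favours the arm that lost more of them.

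At stake is one exploratory table with its tests. It describes when each dose produces recovery. The report could also hold two by-day GI2 tables, from SAP 9.1.2 and 9.3.8, that disagree because their denominators differ.

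**Working it through.** The plan gives no figure for this endpoint, so there is none to reproduce.

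**Inputs from the documents.** 44 mITT patients per arm is the lower planned size (Protocol 9.2, SAP 4.2). About 20% censored within 240 hours, independently and exponentially, is the sample-size assumption in Protocol 9.2. The Weibull shape and scale are not given.

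**Assumptions made here.** The 9.3.8 numerator is read as cumulative, and patients who have achieved GI2 are kept in both numerator and denominator. Other assumptions are stated at each step.

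**Step 1, direction.** Let N be the arm size, E the number with GI2 by the day, and L the number who left without GI2. The 9.3.8 proportion is E/(N − L); the full-arm proportion is E/N. Their difference is E·L / [N(N − L)], which is positive whenever E and L are positive.

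**Step 2, illustration of unequal informative loss.** N = 44 and E = 32 in both arms. Assume 9 leavers in arm X (20% of 44 is 8.8), 3 in arm Y, and that none of them would have recovered.

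| | Arm X | Arm Y |
|---|---|---|
| GI2 achieved | 32 | 32 |
| Left unrecovered | 9 | 3 |
| Stayed unrecovered | 3 | 9 |
| 9.3.8 proportion | 32/35 = 91.4% | 32/41 = 78.0% |
| Full arm | 32/44 = 72.7% | 32/44 = 72.7% |

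The gap is 13.4 points. An unstratified test of 32/35 against 32/41 gives p = 0.11 (z test) or 0.13 (Fisher), so this example would not itself reach significance.

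**Step 3, effect on the test in an extreme case.** Assume true recovery of 70% in both arms. One arm loses 10% or 20% of its patients, all unrecovered, and the other loses none. Rejection rates are from 20,000 simulated trials of an unstratified two-proportion z test, used as a stand-in for the CMH test:

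| Per arm | 9.3.8, 10% loss | 9.3.8, 20% loss | Full arm, either loss |
|---|---|---|---|
| 44 | 13% | 49% | about 5% |
| 85 | 20% | 71% | about 5% |

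**Step 4, loss independent of recovery.** Assume Weibull recovery with shape 2 and RMST to 240 h of 120 h, which gives scale s = 137.2 h. Loss acts only before GI2, at rate λ = −ln(0.8)/240 = 0.00093 per hour. The quantities at hour d are:

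- true proportion: F(d) = 1 − exp[−(d/s)²]
- achieved and observed: E(d) = ∫₀ᵈ f(u) e^(−λu) du, where f is the Weibull density
- still present and unrecovered: R(d) = exp[−(d/s)²] e^(−λd)
- 9.3.8 proportion: E/(E + R); fixed-denominator proportion: E

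| Hour | True | 9.3.8 | Fixed denominator |
|---|---|---|---|
| 72 | 24.1% | 24.5% | 23.0% |
| 120 | 53.4% | 54.5% | 49.9% |
| 168 | 77.7% | 78.8% | 71.1% |
| 240 | 95.3% | 95.8% | 85.8% |

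Here 9.3.8 reads about 1 point high at most, and the fixed denominator reads up to 9.5 points low.

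**Step 5, unequal independent loss.** Keep recovery identical and set λ for 20% loss in one arm and 7% in the other (−ln(0.93)/240 = 0.00030). At 240 h, 9.3.8 gives 95.8% against 95.5%. The fixed denominator gives 85.8% against 92.1%, a false gap of 6.3 points against the arm with more loss.

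**The case against.** The strongest reply is that 32/44 is not observed truth. It counts every leaver as a failure. The 13-point gap therefore rests on the assumption that no leaver would have recovered, and it turns a planning figure for independent censoring into a 9-against-3 informative loss for which the documents give no rate. This stands, and Steps 4 and 5 bear it out: under independent loss the SAP rule is close to the truth and a fixed denominator is worse. A reader might infer that replacing one denominator by the other cures the problem. It does not.

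Exposure is also limited. Patients who stop treatment are still followed for GI2, and patients discharged before a first bowel movement are contacted daily to Day 10 (Protocol 8.1.1.1). Only withdrawal or loss before then should shrink the denominator. This stands, although withdrawal for safety remains open.

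Kaplan-Meier curves and the cumulative table in SAP 9.1.2 already exist. That helps the reader of the report but does not alter the proportion tested under 9.3.8.

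Three further inferences go beyond the documents:

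- **That the cumulative proportion can fall.** This needs patients who achieved GI2 and then left to be dropped. SAP 9.3.8 does not say so; it is silent.
- **That the SAP plainly contradicts the Protocol.** Protocol 9.4 says missing data are not replaced and leaves detail to the SAP, and SAP 9 allows exceptions to the mITT. The day-specific denominator is an unexplained choice, not a breach of an explicit rule.
- **That dose selection is compromised.** Protocol 4.2 does link the design to choosing a dose, but the planned dose-response test is the RMST contrast, which censors leavers.

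**Conclusion.** The concern holds in a limited form. The direction is certain, by arithmetic: each unrecovered leaver raises the 9.3.8 proportion above the full-arm proportion. The size depends on why patients leave. It can be large when loss is informative and unequal: 13 points in the illustration, with false-positive rates of 13% to 71% in the one-sided-loss scenarios of Step 3. It is about 1 point when loss is independent of recovery, under assumed Weibull inputs that the documents do not supply. The documents do not say which situation will arise.

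The endpoint is exploratory, and the primary RMST analysis does not use this denominator. The wording is still worth changing before unblinding, because the rule is tested at each postoperative day and the treatment of leavers is unstated.

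The mITT wording in SAP 5.1 needs attention at the same time. If it is read as requiring a recorded food time and bowel-movement time, unrecovered patients are removed before 9.3.8 applies, and an mITT denominator would not bring them back.

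**What to change.** In SAP 9.3.8:

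1. Remove the stay-in-study denominator. State that GI2, once achieved, counts as achieved on all later days, whether or not the patient then leaves.
2. Report by arm the Kaplan-Meier cumulative probability of GI2 at the end of each day, with the Protocol's censoring at the last nonmissing postbaseline assessment.
3. Beside it, show the proportion with all treated randomised patients in the arm as a fixed denominator and unrecovered leavers counted as not achieved. Label it a conservative sensitivity analysis. If the daily CMH tests are kept on this version, give them the same label.
4. List the number of unrecovered leavers by arm and day, so that a reader can judge whether loss was unequal.

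In SAP 5.1, state that the three-component wording does not remove a patient who lacks a food or bowel-movement time because recovery had not occurred.

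**Cost.** SAP wording and one table program, with no new data. The fixed-denominator figures will be lower and can penalise an arm with more non-informative loss, which is why both versions are shown.

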#### **9.3.8.1 Analysis**

The proportion will be analyzed at each postoperative day in the same way as described in section 9.2.2.1.

### **9.3.9 Proportion of Patients who Receive Concomitant Medication that May Have a Laxative Effect**

The proportion of patients who received concomitant medication during study drug exposure that may have a laxative effect will be calculated. Concomitant medication with a laxative effect can be bisacodyl, macrogol and docusate sodium, but is not limited to these. They will be identified and finalized by the Shionogi Medical Monitor prior to database lock and unblinding.

#### **9.3.9.1 Analysis**

The proportion will be analyzed in the same way as described in section 9.2.2.1.

### **9.3.10 Effect of Prior Surgery on the GI2 Endpoint**

The proportion of patients who achieved of GI2 until 240 hours (yes/no) by prior surgery (no prior surgery, 1 prior surgery or 2 prior surgery) will be calculated. Prior surgeries can be any abdominal surgery except: gastrectomy, gastric bypass, gastric sleeve, lap banding, pancreatic resection, hepatectomy, intestinal transplant. Prior surgeries will be identified and finalized by the Shionogi Medical Monitor prior to database lock and unblinding.

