9.2 Sample Size Determination

The planned sample size of between 44 and 85 patients per treatment in the mITT Population was determined by a simulation study with 10,000 iterations to provide 80% power to demonstrate the linear dose-response relationship between treatment groups (3 naldemedine groups and placebo group) in the primary endpoint at a 2-sided significance level of 0.05. In total, approximately 200 to 340 patients in the study will be required.

The simulation estimated 44 patients per treatment group to see a linear trend in the restricted mean survival time (RMST) up to 240 hours for the time to the event of GI2 across a 24-hour difference between naldemedine 5 mg and placebo under 80% statistical power at a 2-sided significance level of 0.05. Eighty-five patients per treatment group will be required to see a linear trend in RMST up to 240 hours across an 18-hour difference between naldemedine 5 mg and placebo. In addition, the time to the event of GI2 in each group follows the Weibull distribution by referring to the survival curve for the time to the event of GI2 shown in the alvimopan package insert. It was assumed that an independent censoring followed an exponential distribution with a rate such that approximately 20% of patients were censored within 240 hours.

The final sample size will be dependent on the enrollment rate during the fixed enrollment period. A minimum of 44 patients per group in the mITT Population is desired.

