9.4.5.3 Exploratory Efficacy Endpoints

Exploratory efficacy endpoints will be as follows:

- Time from the end of surgery (as defined for the primary endpoint) to time to discharge readiness (defined as GI recovery based on the clinical judgment of the investigator)
- Time from the end of surgery (as defined for the primary endpoint) to time of actual discharge (departure) from the hospital
- Proportion of patients with prolonged hospital stay (defined as hospitalization for ≥ 7 days postoperatively) due to GI dysfunction
- Time from initial insertion of the nasogastric tube to removal of the nasogastric tube

- Proportion of patients with abdominal distention on Day 1 through the day on which GI2 is achieved
- Proportion of patients with nausea on Day 4 through day of discharge
- Proportion of patients with vomiting on Day 4 through day of discharge
- Proportion of patients who achieve GI2 in each treatment group by postoperative day
- Proportion of patients who receive concomitant medication that may have a laxative effect
- Effect of prior surgery (yes/no) on the GI2 endpoint

For time from the end of surgery to time to discharge readiness and to time of actual discharge from the hospital, the same KM approach as used for the primary efficacy analysis will be performed. The proportion of patients for each of the other parameters will be summarized by treatment group.

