## 6.2 Statistical Testing

All statistical tests will be performed at the 2-sided significance level of 0.05, unless otherwise noted. No multiplicity adjustment will be made in this study.

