### **9.1.3 Subgroup Analysis**

RMST will be calculated and two types of KM curve with 95% confidence bound and point estimate line only will be provided by following subgroups.

- Surgical procedure (Small bowel resection with primary anastomosis, large bowel resection with primary anastomosis, or radical cystectomy requiring bowel transection with primary anastomosis)
- Prior surgery (No prior surgery, 1 prior surgery, 2 prior surgeries)
- Epidural anesthesia (yes/no)
- Enhanced recovery protocol (all aspects of ERP versus those that had only the 3 that were mandated)

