#### **9.3.10.1 Analysis**

Pairwise comparison as Cochran Mantel Haenszel test adjusted by prior surgery will be applied to the proportion.

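### The prior-surgery endpoint is tested only on GI2 yes/no at 240 hours, which discards the timing; an RMST difference between patients with and without prior surgery should carry the analysis (minor, exploratory endpoint)

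*SAP*

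**What the plan says.** Protocol 9.4.5.3 lists "Effect of prior surgery (yes/no) on the GI2 endpoint" among the exploratory endpoints. Protocol 9.4.5.1 and SAP 9.1 define GI2 as a time from the end of surgery, and the primary analysis compares RMST to 240 hours.

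SAP 9.3.10 turns the prior-surgery endpoint into "The proportion of patients who achieved of GI2 until 240 hours (yes/no) by prior surgery", with three levels (none, 1 or 2). SAP 9.3.10.1 then states: "Pairwise comparison as Cochran Mantel Haenszel test adjusted by prior surgery will be applied to the proportion". No other test is attached to the endpoint.

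SAP 9.1.3 lists prior surgery as a subgroup factor for which "RMST will be calculated and two types of KM curve" will be provided, with 95% confidence bounds on one type of curve. It plans no RMST difference between levels, no interval for one, and no test.

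Protocol 9.2 sizes the trial on Weibull event times whose parameters are not given, with censoring such that "approximately 20% of patients were censored within 240 hours". SAP 9.3.10 does not say whether a patient censored before 240 hours counts as 'no', as missing, or not at all.

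**The concern.** GI2 is about how soon the gut recovers. If nearly all patients recover within ten days when followed that long, a yes/no outcome at 240 hours says little about speed, and any 'no' group may consist largely of censored patients. A non-significant result could then be read as evidence that prior surgery makes no difference, although the test had little chance of showing one. The data for a sharper analysis are already collected, and the method is already in the SAP.

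**Working it through.** **Inputs.** From the documents: "All statistical tests will be performed at the 2-sided significance level of 0.05, unless otherwise noted" (SAP 6.2). From Protocol 9.2: a trend in RMST "across a 24-hour difference between naldemedine 5 mg and placebo" with 44 per group, "under 80% statistical power at a 2-sided significance level of 0.05"; and 18 hours with 85 per group. The contrast is (-3, -1, 1, 3). Not in the documents: the Weibull shape and scale, the share expected to reach GI2 by 240 hours, the share with prior surgery, and any prior-surgery effect. These are assumed below and shown as ranges.

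**1. The plan's sizes.** With equal steps across a difference d, the contrast is 3d + d/3 = 10d/3 and its standard error is SD × √(20/n). For 80% power the ratio must be 1.960 + 0.842 = 2.802.
- 24 h, n = 44: SD = 80 / (2.802 × √(20/44)) = 80 / 1.889 = 42.4 h.
- 18 h, n = 85: SD = 60 / (2.802 × √(20/85)) = 60 / 1.359 = 44.2 h.

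The two sizes agree with each other. Without the Weibull parameters neither can be reproduced independently. I therefore took placebo RMSTs of 80–160 h and solved the shape to give 80% at 44 per group and 24 h; the same curves then give about 80–82% at 85 per group and 18 h. Two readings of the 20% were used: 20% of censoring times fall before 240 h, or 20% of patients are censored before their event.

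**2. What the cut leaves.** Example: placebo RMST 100 h, shape 2.4. The scale is 100/Γ(1 + 1/2.4) ≈ 112.8 h, so the share reaching GI2 by 240 h without censoring is 1 − exp(−(240/112.8)^2.4) ≈ 99.8%. Over all calibrated curves it is 97.0–99.8% on placebo and 99.9–100% on 5 mg. If censored patients count as 'no', the shares are 77–93% and 81–95%.

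**3. 5 mg versus placebo, 24 h, 44 per group.**
- RMST: 24 / (42.4 × √(2/44)) = 24 / 9.04 = 2.66; power = Φ(2.66 − 1.96) = 76%. Weibull variances give 74–76%, and simulation (4,000 runs) 75–77%.
- Binary, censored as 'no', same example with 20% censored before the event on placebo: 79.9% versus 84.3%. Pooled SE = √(0.821 × 0.179 × 2/44) = 0.082; power ≈ Φ((0.044 − 1.96 × 0.082)/0.082) ≈ 8%. Over all curves: 6–11%.
- Binary, true status known for everyone: about 0.1%.
- Lower doses by RMST on the same linear trend: about 39% for a 16 h difference and 12–13% for 8 h. The common SD of 42.4 h would give 42% and 14%; Weibull slower arms are more variable.
- At 85 per group and 18 h: simulated stratified binary test 7–8%, RMST about 78%.

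**4. Prior surgery itself.** A Cochran-Mantel-Haenszel test adjusted by prior surgery compares treatments within prior-surgery levels. With no treatment effect and a true prior-surgery effect of 24 or 48 h, it rejected in 4.6–5.1% of simulated runs, which is the alpha level. So step 3 is not power for an effect of prior surgery. For a direct comparison of none versus any:
- Assumed split 105/71 of 176 (4 × 44), 24 h: 24 / (42.4 × √(1/105 + 1/71)) = 24 / 6.51 = 3.68; RMST power = Φ(1.72) ≈ 96%. A binary test on the same split has 7–14%.
- Assumed total 176–340, prior-surgery share 20–50%, effect 12–24 h: binary about 5–20%, RMST 29% to over 99%. For 18 h at 176 patients, RMST power runs from 52–55% (20% share) to 81% (50% share).

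**The case against.** **The time scale is already covered.** SAP 9.1.3 shows RMST and curves by prior-surgery level, so a reader would see any large gap. This stands in part: what is missing is only the difference, its interval and a test. The one p-value offered is still on the weaker scale.

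**The protocol points to proportions.** Protocol 9.4.5.3 assigns the Kaplan-Meier approach to two discharge endpoints and says the remaining parameters are summarised as proportions. Protocol 9.4.5.1 also uses GI2 achieved or not in several supplementary tables. But an effect of a baseline factor on a time is not itself a proportion, so the generic sentence fits this endpoint poorly and does not justify the cut.

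**Stronger readings that do not hold.**
- A reader might infer that the prior-surgery endpoint has 10% power where RMST would have 75%. Those figures are for 5 mg versus placebo. The documents give neither a prior-surgery effect nor its prevalence.
- A reader might infer that almost everyone passes the cut, or that the test mainly compares censoring. Neither is stated. The first follows from calibrated curves without censoring, or if the mITT definition in SAP 5.1 requires all three time components. The second requires that censored patients count as 'no'.

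**Reusing 9.1.1 unchanged would not help.** With prior-surgery level as the stratum, it would again compare treatments and largely repeat the primary pairwise analysis. Its equal-weight sum also suffers from a sparse level: at SD 42.4 h, 44 per group and 24 h, assumed none/1/2 splits of 50/30/20, 60/30/10, 70/20/10 and 60/35/5 give 70%, 54%, 50% and 36%. This objection stands and shapes the fix.

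**Conclusion.** The point holds in a limited form. The only formal analysis of the prior-surgery endpoint uses a 240-hour yes/no outcome that discards timing, and the loss is large under every calibrated curve examined. The ranges rest on Weibull shapes inferred from the stated sizes, on counting censored patients as 'no' and, for prior surgery itself, on an assumed prevalence and effect. The treatment figures must not be quoted as power for prior surgery. Severity is minor: the endpoint is exploratory, no decision rule depends on it, and the primary analysis is untouched.

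**What to change.** In SAP 9.3.10.1, make the analysis the difference in RMST to 240 hours between patients with no and with any prior surgery (the protocol's yes/no factor), with a 95% CI and test. Use the Kaplan-Meier estimate and censoring rule of 9.1 and 9.1.1, stratify by treatment group, and weight strata by size or precision rather than summing them equally. Show the none/1/2 levels, and treatment differences within level, descriptively. Keep the 240-hour proportions as a table without a test, and state how censored patients are counted in it.

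The cost is SAP wording and reuse of the RMST program in SAP 13.2 with a different grouping; no new data and no protocol amendment are needed. There are two limits. Prior surgery is not randomised, so the contrast is an association open to confounding. The level with 2 prior surgeries may also be too sparse to report more than descriptively.

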Exploratory	
 To compare the efficacy of naldemedine 1.25 mg, 2.5 mg, and 5 mg and placebo for the exploratory endpoints Time from the end of surgery to time to discharge readiness Time from the end of surgery to time of actual discharge (departure) from the hospital Proportion of patients with prolonged hospital stay due to gastrointestinal dysfunction Time from initial insertion of the nasogastric tube to removal of the nasogastric tube Proportion of patients with abdominal distention on Day 1 through the day on which GI2 is achieved Proportion of patients with nausea on Day 4 through day of discharge Proportion of patients with vomiting on Day 4 through day of discharge Proportion of patients who achieve GI2 in each treatment group by postoperative day Proportion of patients who receive concomitant medication that may have a laxative effect Effect of prior surgery (yes/no) on the GI2 endpoint
Pharmacokinetics	
 To characterize the pharmacokinetics (PK) profile of naldemedine 1.25 mg, 2.5 mg, and 5 mg and its metabolite (nor-naldemedine) for the PK endpoints Plasma drug concentrations of naldemedine and nor-naldemedine on: 
 Day 2 immediately before the morning dose Day 3 immediately before the morning dose and 1 hour and 2, 4, 8, and 12 hours after the morning dose before administration of the evening dose Day 4 immediately before the morning dose PK parameters of naldemedine and nor-naldemedine (C_{max}, T_{max}, AUC, CL/F, $MR_{M/U}$, C_{max}, and $MR_{M/U}$, AUC)
Safety	
 To compare the safety of naldemedine 1.25 mg, 2.5 mg, and 5 mg and placebo for the safety endpoints Incidence of treatment-emergent adverse events, including those that are serious and those that result in discontinuation of study treatment

	
• Proportion of patients with clinically significant changes in clinical laboratory tests, vital signs, and ECGs• Change from baseline in pain intensity, as assessed on a Numerical Pain Rating Scale (NPRS)• Total dose of intra- and postoperative opioid analgesics in morphine milligram equivalents (MMEs)
--	--

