5.2 Exclusion Criteria

Patients are excluded from the study if any of the following criteria apply:

Medical Conditions

- 1. Scheduled to undergo a total colectomy or any procedure that results in a colostomy or ileostomy.
- 2. Scheduled for endoscopic or laparoscopic surgery.
- 3. Complete bowel obstruction.
- 4. Complicated inflammatory bowel disease (such as ulcerative colitis or Crohn's disease).
- 5. More than 2 prior major abdominal surgeries (eg, gastrectomy, gastric bypass, gastric sleeve, lap banding, pancreatic resection, hepatectomy, intestinal transplant).

Prior and Concomitant Therapy

- 6. More than 3 doses of an opioid (regardless of the route of administration) during the 7 days prior to surgery.
- 7. Chemotherapy within 4 weeks prior to surgery; otherwise, patients with cancer are eligible.
- 8. Scheduled to receive chemotherapy, immunotherapy, or radiation therapy intraoperatively or within 14 days after surgery; otherwise, patients with cancer are eligible.
- 9. Any prohibited medication within 14 days prior to the first dose of study treatment as specified in [Section 6.5](#).

Prior and Concurrent Clinical Study Experience

- 10. Exposure to an investigational drug within 90 days prior to the start of Screening.
- 11. Prior exposure to naldemedine.

Diagnostic Assessments

12. Severe hepatic impairment.

Other Exclusions

13. Pregnancy or lactation.
14. Presence of peritoneal catheter (eg, for dialysis or chemotherapy).
15. Any other reason considered by the investigator or qualified designee to make the patient ineligible to take part in the study.

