8.1.3.6 Effect of Prior Surgery on G12 Endpoint

The effect of prior surgery (yes/no) on the GI2 endpoint will be assessed.

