**Table 7 Category**

Data	Category
Age	18<= x < 65, 65 < x < 74, 75<=x<=80
Sex	Male, Female
Surgical procedure	Small bowel resection with primary anastomosis, large bowel resection with primary anastomosis, or radical cystectomy requiring bowel transection with primary anastomosis
Fertility status for females	Surgically sterile, post-menopausal, potentially able to bear children
Race	American Indian or Alaska Native, Asian, Black or African American, Native Hawaiian or Other Pacific Islander, White, Other, Not provided
Ethnicity	Hispanic or Latino, Not Hispanic or Latino, Unknown, Not provided
Elements of the enhanced recovery protocol	(required) Early removal of the nasogastric tube defined as removal of the nasogastric tube at the end of surgery, early ambulation defined as ambulation on Day 1, early diet advancement on Day 1  (non-required) Antibiotic prophylaxis, preoperative carbohydrate drink, epidural anesthesia in addition to general anesthesia, chewing gum postoperatively
Elements of the enhanced recovery protocol (binary)	All non-required (defined as all of 4 non-mandated ERP elements), not all non-required (defined as otherwise all non-required)
Epidural anesthesia	Yes (defined as Yes in epidural anesthesia in addition to general anesthesia in ERP), No (defined as No in epidural anesthesia in addition to general anesthesia in ERP)
Prior surgery	No prior surgery, 1 prior surgery and 2 prior surgeries
Treatment compliance	x <80%, 80% <= x <=100%, 100% < x

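### The SAP counts eligible patients with prior major abdominal operations as having had no prior surgery, and its test for the prior-surgery endpoint compares treatments instead

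*SAP*

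**What the plan says.** The protocol lists as an exploratory endpoint (Sections 1.1 and 3): "Effect of prior surgery (yes/no) on the GI2 endpoint". Section 8.1.3.6 adds: "The effect of prior surgery (yes/no) on the GI2 endpoint will be assessed". Exclusion criterion 5 in Section 5.2 reads "More than 2 prior major abdominal surgeries (eg, gastrectomy, gastric bypass, gastric sleeve, lap banding, pancreatic resection, hepatectomy, intestinal transplant"). Patients with none, one or two such operations can therefore enrol.

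The SAP defines prior surgery in Section 7.2 (baseline table) and again in Section 9.3.10 (this endpoint), in the same words: "Prior surgeries can be any abdominal surgery except: gastrectomy, gastric bypass, gastric sleeve, lap banding, pancreatic resection, hepatectomy, intestinal transplant". Neither section gives a reason. Both leave identification of prior surgeries to the medical monitor before database lock.

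The levels in Table 7 are "No prior surgery, 1 prior surgery and 2 prior surgeries", and SAP 9.1.3 uses the same three for RMST and Kaplan-Meier displays. SAP 9.3.10 tabulates the proportion achieving GI2 by 240 hours at each level. The only test is in 9.3.10.1: "Pairwise comparison as Cochran Mantel Haenszel test adjusted by prior surgery will be applied to the proportion".

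**The concern.** There are two separate faults.

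The first is the definition. The operations the protocol gives as examples of major abdominal surgery are exactly those the SAP stops counting. Patients with a major operation behind them would sit in the comparison group labelled as having none, in every output that uses the variable.

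The second is the test. The endpoint is the effect of prior surgery on GI2, but the specified test compares treatment groups within levels of prior surgery. The report would then print a treatment p-value under the heading of the effect of prior surgery, with no estimate of that effect and no interval for it.

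**Working it through.** The plan gives no figure for this endpoint, so there is none to reproduce. The check compares texts first and then illustrates the consequences.

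**1. The lists.** Protocol 5.2 names seven operations. SAP 7.2 and 9.3.10 except seven. All seven match, in the same order, so this is not a slip in one place.

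**2. How eligible patients are coded under the SAP.**

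| Earlier abdominal operations | Eligible under criterion 5? | SAP level |
|---|---|---|
| One or two listed, no others | Yes | No prior surgery |
| One listed, one unlisted | Yes | 1 |
| Three or more unlisted, at most two of them major | Yes | None available |

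The last row arises because criterion 5 limits major operations only, while the SAP levels stop at two and count unlisted operations, major or not.

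**3. What the 9.3.10.1 test compares.** SAP 9.2.2.1 says: "Pairwise comparison as Cochran Mantel Haenszel test adjusted by surgical procedure will be applied to the proportion". Section 9.3.10.1 has the same form with a different stratum. SAP 9.1.1 uses pairwise comparison for pairs of treatment groups. A CMH test conditions on its stratum and does not test it. On expected counts with no treatment effect and a prior-surgery effect of 0, 10, 20 or 30 points (assumed), the CMH statistic is 0 in every case, at both 44 and 85 patients per group.

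**4. Simulation.** Inputs: 44 and 85 per group come from the sample-size sections. All else is assumed: no treatment effect, 40% with prior surgery, procedures split 20/60/20%, GI2 by 240 hours in 80% without prior surgery and 80, 70 or 60% with it. There were 4,000 runs per setting, so the Monte Carlo standard error at 5% is √(0.05 × 0.95 / 4000) = 0.34 points. Entries are rejection rates at 0.05.

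| GI2 with prior surgery | SAP 9.3.10.1 test*, n = 44 | n = 85 | Yes/no CMH†, n = 44 | n = 85 |
|---|---|---|---|---|
| 80% | 5.3% | 5.2% | 5.4% | 5.5% |
| 70% | 4.8% | 4.7% | 31.3% | 54.1% |
| 60% | 5.1% | 5.0% | 79.7% | 97.7% |

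\* 5 mg versus placebo, stratified by prior surgery (yes/no here).
† Prior surgery yes versus no, stratified by treatment and procedure.

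The planned test stays at its nominal level whatever prior surgery does to GI2.

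**5. Dilution from the coding.** Let w be the share of the recorded no-surgery group whose only operations are listed, and d the true yes/no difference. If listed and unlisted operations act alike, the observed difference is (1 − w) × d. For an assumed d = 20 points:

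- w = 2%: 0.98 × 20 = 19.6
- w = 5%: 0.95 × 20 = 19.0
- w = 10%: 0.90 × 20 = 18.0
- w = 20%: 0.80 × 20 = 16.0

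Equivalently, w = qf / ((1 − q) + qf), where q is the share of patients with any prior abdominal surgery and f the share of those with listed operations only. With q = 0.2 and f = 0.1, w = 0.02/0.82 = 2.4% and 19.5 points remain. With q = 0.6 and f = 0.5, w = 0.30/0.70 = 42.9% and 11.4 remain. The documents give neither q nor f.

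**The case against.** The strongest reply is that the protocol never promised a contrast between prior-surgery levels. Its exploratory objective is to compare doses and placebo, Section 9.4.5.3 promises only a summary by treatment group for this endpoint, and Section 8.1.3.6 says no more than that the effect will be assessed. SAP 9.3.10 gives proportions by level, and 9.1.3 gives RMST and Kaplan-Meier curves with confidence bounds. On that view a descriptive assessment exists and a formal contrast is a preference.

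Part of this stands. The SAP is not silent, and a descriptive reading of the protocol is possible. But the descriptive outputs use the same coding, their bounds are not intervals for a difference between levels, and a treatment p-value does not assess prior surgery. Reading effect as effect modification does not help: CMH does not test homogeneity, and no interaction test is planned.

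Other points are fair. The levels 0, 1 and 2 collapse to yes/no, so the finer grouping does little harm in itself. Nothing shows that patients without a level would enrol. The dilution and power figures rest on assumed inputs, and at a share of 2% to 5% the dilution is negligible.

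The medical monitor's review is not a remedy as written. SAP 9.3.9 states that its laxative examples are not exhaustive, whereas the surgical exception has no wording that lets the reviewer set it aside.

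**Conclusion.** Both faults hold, at minor severity. The definition conflicts with the protocol without explanation, and the test in 9.3.10.1 does not address the endpoint it is filed under. These conclusions rest on the texts and the form of the test, not on the assumed rates.

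The reach is one exploratory endpoint, one descriptive subgroup of the primary endpoint and one baseline row. Primary and secondary tests, sample size and alpha are unaffected. The direction and size of any bias cannot be derived from the documents; the dilution in the working requires that listed and unlisted operations affect GI2 alike. The listed operations remain visible in the medical-history summary, so the variable could be rebuilt later, but the planned outputs would not use it.

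**What to change.** Before unblinding:

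- In SAP 7.2, 9.1.3, 9.3.10 and Table 7, count the seven listed operations as prior abdominal surgery. Major and other abdominal surgery can also be shown separately.
- Use yes/no for the endpoint, as in the protocol, and 0, 1, and 2 or more for the displays.
- In 9.3.10.1, estimate the yes/no difference in GI2 by 240 hours with a 95% CI, stratified by treatment group and surgical procedure. Name the estimator, for example the Mantel-Haenszel risk difference alongside the CMH test. Label the result exploratory and non-randomised, and show treatment differences within each prior-surgery level.
- If the exception is deliberate, state the reason and rename the variable to say what it counts.

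The cost is SAP wording and a little programming. No new data are needed, since footnote d of the protocol's Schedule of Activities already has all past surgeries recorded. The stratification gives 4 × 3 = 12 strata, averaging 176/12 = 14.7 patients at 44 per group and 340/12 = 28.3 at 85, so some will be sparse.
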